3.4.4.2 Dose Modification for Toxicity Management: Blood Chemistry Abnormalities

If total bilirubin is $> 2 \times \text{ULN}$ at the central laboratory:

- Do not administer study drug at next dosing visit.
- Repeat total bilirubin as well as direct and indirect values, liver function tests (LFTs; including AST, ALT, and alkaline phosphatase), evaluate reticulocyte count immediately to confirm abnormalities. Repeat all tests again in 1 week.
 - If bilirubin remains $> 2 \times \text{ULN}$ (not due to Gilbert's syndrome or hemolysis) do not administer study drug at next dosing visit
 - If bilirubin returns to within normal limits ($< \text{ULN}$), study drug may be administered at next scheduled dosing visit
 - If repeat bilirubin is $< 2 \times \text{ULN}$ but $> \text{ULN}$; hold dose and discuss with medical monitor.

Study drug will be discontinued in subjects who miss 2 consecutive scheduled doses of study drug due to elevated bilirubin (see section 4.7).

If ALT or AST is $> 3 \times \text{ULN}$, refer to Guidance for Abnormal Liver Function Tests in Appendix J.

Study drug will be discontinued in subjects who miss 3 consecutive scheduled doses of study drug due to elevated ALT or AST (see 4.7).

As indicated in the Guidance for Abnormal Liver Function Tests (Appendix J), additional laboratory tests may be ordered from Quintiles Laboratory as needed. The LFTs that the guidelines require to be repeated are AST, ALT, total bilirubin and alkaline phosphatase.

Additional tests may be ordered as required by investigators, these tests include: CPK, GGT, INR, PT, albumin, EBV, CMV, hepatitis A antibody, hepatitis B surface antigen, hepatitis B core antibody and hepatitis C antibody.

3.4.5 Concomitant Medications

All concomitant medications, including herbal products, used by the patient from screening through Study Day 350 will be recorded on the case report form. The concomitant administration of IVIG is allowed.

Patients may not receive the following from screening through Study Day 350:

1. Investigational agents (eg, rituximab for myositis);
2. Any live attenuated virus vaccine;
3. Hydroxychloroquine > 600 mg/day, mycophenolate mofetil > 3 g/day, methotrexate > 25 mg/week, leflunomide > 20 mg/day, azathioprine > 3 mg/kg/day; or
4. Any dose of cyclophosphamide, cyclosporine, or thalidomide.

Corticosteroid doses may not exceed 35 mg/day of prednisone or an equivalent dose of another corticosteroid. Corticosteroid doses must remain constant from 14 days before Study Day 0 through Study Day 196. Thereafter, corticosteroid doses may be increased, tapered, and discontinued as considered appropriate by the investigator.

Patients may receive medications to treat adverse events as deemed necessary by the investigator or the patient's physician.

See Section 3.4.2 for guidance in handling clinical deteriorations.

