2.4 Overview

2.4.1 Study Design

The study is a multicenter, randomized, double-blind, placebo-controlled, dose-escalation study to evaluate the safety and tolerability of multiple IV doses of MEDI-545 in adult patients with DM or PM who have low/undetectable or high level of expression of mRNA for type I IFN-inducible genes in whole blood or muscle at the time of screening. Approximately 20 investigative sites in the United States of America (USA) will participate in the study. A total of 32 evaluable patients with high level of expression of mRNA for type I IFN-inducible genes (ie, gene signature positive) will be randomized in a 3:1 ratio to initially receive MEDI-545 (0.3, 1.0, 3.0, or 10.0 mg/kg) or placebo every 2 weeks for 12 weeks for a total of 7 doses. An additional cohort (Dose Cohort 3B) of 8 evaluable patients with low/undetectable or negative expression of type I IFN-inducible genes (ie, gene signature negative) will be randomized in a 3:1 ratio to initially receive MEDI-545 (3.0 mg/kg) or placebo every 2 weeks for 12 weeks for a total of 7 doses, with 6 patients receiving MEDI-545 and 2 patients receiving placebo. In each dose cohort, 6 patients will receive MEDI-545 and 2 patients will receive placebo. Thereafter (2 weeks after the 7th dose), in each of the 5 dose cohorts, patients randomized to MEDI-545 will continue to receive the same dose of MEDI-545 over an additional 12 weeks (7 doses) and patients randomized to placebo will receive MEDI-545, at the dose specified in the dose cohort, every 2 weeks for an additional 12 weeks (7 doses) for a total of 26 weeks (14 doses).

All patients should receive their usual medications in unchanged doses during the entire treatment period. If a patient clinically deteriorates in the judgment of the investigator the investigator is permitted to add new or increase existing immunosuppressive medications, as long as no prohibited medications are added (see Section 3.4.5). Concurrent immunosuppressive therapy may be tapered and discontinued, according to the investigator's judgment, during the follow-up period.

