Patients are considered evaluable if they receive the first 4 doses of study drug (MEDI-545 or placebo) and complete the required evaluations, or if they discontinue study drug administration at any time for safety reasons. Nonevaluable patients may be replaced to maintain a size of at least 8 patients per dose cohort. Data from all patients will be included in safety analyses. A dose cohort may be expanded by up to 4 additional patients (for a maximum of 20 additional patients in total) if eligible patients are in screening at the time 8 patients have been randomized into the dose cohort.

Study drug administration will start on Study Day 0 and continue through Study Day 182. At the end of the treatment period, patients will be followed for 24 weeks, through Study Day 350. Safety parameters including assessments of AEs and SAEs will be assessed at every study visit from the signing of the informed consent through Study Day 350. Disease activity will be assessed throughout the treatment period and during follow-up. Patient evaluations are described in Table 4 and Table 5.

Decisions regarding dose escalation will be made by the Medical Monitor based on the review of all cumulative, blinded safety information which includes the safety data through Study Day 42 from the first 8 evaluable patients in each of the preceding lower dose cohorts (Section 4.9).

The study schema is described in Figure 1.

[figure not shown]

Figure 1 Study schematic

Patients who participate in this study may have the option of entering a long-term safety study (MI-CP212). This includes both MEDI-545 and placebo patients, but excludes patients who discontinued from previous MEDI-545 clinical studies for safety reasons. Patients must complete the treatment period and follow up through Day 266 of this study to participate in MI-CP212. Patients must also qualify for the long-term safety study (following written informed consent), as per the MI-CP212 protocol inclusion and exclusion criteria. If patients qualify, they will receive open-label MEDI-545. Patients may be treated for approximately 3 years and may be followed for an additional 3 months following the last dose of IV MEDI-545.

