3.1.2 Exclusion Criteria

Patients must have *none* of the following criteria:

1. Receipt of MEDI-545 in any previous clinical study or prior randomization into the trial;
2. History of allergy or reaction to any component of the study drug formulation;
3. Inclusion body myositis, cancer-associated myositis, myositis associated with another connective tissue disease, environmentally-associated myositis, or drug-related myopathy;
4. A history of or a family history of noninflammatory myopathy, scapular winging, atrophy, or hypertrophy of the calf muscles;
5. Receiving prednisone > 35 mg/day (or an equivalent dose of another corticosteroid) within 14 days before Study Day 0;
6. Receiving the following dosages of medications within 28 days before Study Day 0: hydroxychloroquine > 600 mg/day, mycophenolate mofetil > 3 g/day, methotrexate > 25 mg/week, azathioprine > 3 mg/kg/day, or any dose of cyclophosphamide, cyclosporine, or thalidomide;
7. Have received fluctuating doses of antimalarials, mycophenolate mofetil, methotrexate, leflunomide, or azathioprine within 28 days before Study Day 0 or fluctuating doses of corticosteroids within 14 days before Study Day 0;
8. Have received leflunomide > 20 mg/day in the 6 months prior to Study Day 0.
9. Treatment with any investigational drug therapy within 28 days before Study Day 0 or biologic therapies (eg, rituximab) within 30 days or 5 half-lives of the biologic agent, whichever is longer, before Study Day 0;
10. In the investigator's opinion, evidence of clinically significant active infection, including ongoing, chronic infection, within 28 days before Study Day 0;
11. A history of severe viral infection as judged by the investigators, including severe infections of either CMV or the herpes family such as disseminated herpes, herpes encephalitis, ophthalmic herpes;
12. Herpes zoster \leq 3 months prior to Study Day 0;
13. Evidence of infection with hepatitis B or C virus or HIV-1 or HIV-2, or active infection with hepatitis A, as determined by results of testing at screening;
14. Vaccination with live attenuated viruses within 28 days before Study Day 0;
15. Pregnancy (sexually active women, unless surgically sterile or at least 2 years post-menopausal, must have a negative serum pregnancy test at screening and a negative urine pregnancy test prior to study drug administration on Study Day 0);
16. Breastfeeding or lactating women;
17. History of alcohol or drug abuse < 1 year prior to Study Day 0;

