All patients should continue to receive medications they were taking at the time of consent in unchanged doses during the entire treatment; however, if clinical deterioration occurs and additional treatment is warranted in the opinion of the investigator, the investigator is permitted to add new or increase existing immunosuppressive medications, as long as no prohibited medications are added (see Section 3.4.5). Concurrent immunosuppressive therapy may be tapered and discontinued, according to the investigator’s judgment, during the follow-up period.

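### The constant-dose rule to Day 196 names corticosteroids only; other immunosuppressives may be tapered at the investigator's discretion about 14 days before the Day 196 activity evaluation

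*Protocol*

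**What the plan says.** Protocol Section 3.4.5 sets a dated rule for one drug class: "Corticosteroid doses must remain constant from 14 days before Study Day 0 through Study Day 196". It continues: "Thereafter, corticosteroid doses may be increased, tapered, and discontinued as considered appropriate by the investigator". For the other immunosuppressives that section gives only dose ceilings and a list of prohibited agents.

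The general rule for background medication is in Section 2.4.1, repeated in the abstract and, in similar words, in Section 3.4.2: "All patients should receive their usual medications in unchanged doses during the entire treatment period". It is followed by a permission in all three places: "Concurrent immunosuppressive therapy may be tapered and discontinued", at the investigator's "judgment, during the follow-up period". No day number is attached.

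Section 2.4.1 also fixes the periods: "Study drug administration will start on Study Day 0 and continue through Study Day 182", and "At the end of the treatment period, patients will be followed for 24 weeks, through Study Day 350". Table 5 and the visit lists in Section 3.5 place Days 185, 189 and 196 in follow-up.

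Day 196 carries the full activity set: manual muscle testing, extramuscular activity, both global assessments, CLINHAQ and muscle enzymes. It is the evaluation to complete when a patient withdraws between Days 98 and 196, and it triggers the third safety and efficacy interim in Section 5.5. Section 3.3 says these interims inform clinical development decisions.

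**The concern.** Day 196 comes one dosing interval after dose 14, as Day 98 comes one interval after dose 7. The protocol files it under follow-up, but in practice it closes the treatment phase for disease activity, and the corticosteroid rule runs to exactly that day. No reason is given for ending the rule for the other agents two weeks earlier.

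If a non-steroid agent is reduced or stopped in that gap, the change from baseline to Day 196 mixes the effect of MEDI-545 with a permitted change in background therapy. The same applies to the change from Day 98 to Day 196 in patients who switched from placebo. By then every patient is assigned MEDI-545, so no concurrent placebo group shows what the background change alone would do.

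The two rules also sit awkwardly together. Concurrent immunosuppressive therapy ordinarily includes corticosteroids, so the general sentence, read literally, permits from the start of follow-up what Section 3.4.5 forbids until after Day 196.

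**Working it through.** **Inputs.** Last dose Day 182; follow-up 24 weeks, to Day 350 (Section 2.4.1). Visit windows: Day 182 ± 1 day, Day 196 ± 3 days (Section 3.5). Dosing every 14 days from Day 0, 14 doses (Section 3.4.2).

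**1. Where follow-up starts.** The protocol's own figure comes first.
- From Day 182: (350 − 182)/7 = 24.0 weeks, which matches the stated 24 weeks.
- From Day 196: (350 − 196)/7 = 22.0 weeks, which does not match.
- Dose 14 falls on Day 13 × 14 = 182, and 26 weeks × 7 = 182 agrees.

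The treatment period therefore ends at Day 182, and permission to taper begins there.

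**2. The gap before the Day 196 evaluation.**
- Nominal: 196 − 182 = 14 days.
- Shortest with windows: 193 − 183 = 10 days.
- Longest with windows: 199 − 181 = 18 days.
- For comparison, dose 7 is on Day 84, and 98 − 84 = 14 days. Day 98, however, lies inside the treatment period, where discretionary tapering is not allowed.

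**3. Whether an earlier value can stand in.** By the visit lists, Day 182 adds muscle enzymes only. The other five of the six IMACS core measures were last taken on Day 154, which is 196 − 154 = 42 days earlier. Doses on Days 0, 14, …, 140 number 140/14 + 1 = 11, so the Day 154 values follow 11 of 14 doses and do not replace Day 196.

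**4. What may change, and when.**

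| Period | Corticosteroids | Other immunosuppressives |
|---|---|---|
| Before Day 182 | Constant (3.4.5) | Unchanged, except additions or increases for deterioration (3.4.2) |
| Day 182 to Day 196 | Constant by 3.4.5; taper allowed by the literal general sentence | Discretionary taper or stop |
| After Day 196 | Free within limits | Free within limits |

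IVIG is allowed throughout (3.4.5). Medication may be given for adverse events, and Appendix J has methotrexate withheld when transaminases rise.

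**5. Size.** The protocol does not say how many patients take non-steroid agents or how many would taper this early. As an assumption for scale only: if 0, 1 or 2 of 8 patients in a cohort changed IMACS response status for this reason, that cohort's Day 196 proportion would move by 0, 1/8 = 12.5 or 2/8 = 25 points. Nothing in the protocol shows that any patient would.

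**The case against.** The strongest case against is that little hangs on this. The activity measures are exploratory and descriptive, and no formal tests are planned. The placebo-controlled contrast ends at Day 98, and Day 196 is uncontrolled whatever the tapering rule. Section 5.4.3.1 lists changes in immunosuppressive therapy during follow-up as a measure in its own right, so the protocol means to observe tapering. Concomitant medications are recorded through Day 350, so early tapers can be identified. Nothing in the schedule prompts one: Days 185 and 189 have no activity assessment and no medication review. A stricter rule for corticosteroids, which Section 1.1 calls the mainstay of treatment, could be deliberate.

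Most of this stands and limits the point to a minor one. It does not remove it: recording a taper does not recover the value the patient would have had without it, and no reason is given for the different end dates.

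Three stronger inferences are tempting, and the documents do not support them.
- *That background therapy is fixed until Day 182.* It is not. The deterioration exception, IVIG and the management of adverse events can all change it before Day 98 or Day 154. Only discretionary tapering is new after Day 182.
- *That a 14-day gap breaches the protocol's own 28-day standard.* The criterion excluding patients who "Have received fluctuating doses of antimalarials, mycophenolate mofetil, methotrexate, leflunomide, or azathioprine within 28 days before Study Day 0" governs eligibility. It sets no standard for later visits, and it uses 14 days for corticosteroids.
- *That Day 196 results would be materially distorted.* The point shifts above are assumed. Reducing background therapy would also more plausibly hide a benefit than create one.

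**Conclusion.** The gap in the text is real: non-steroid immunosuppressives may be tapered at discretion about 14 days (10 to 18 with windows) before the Day 196 activity evaluation. This rests on the treatment period ending at Day 182, which the 24-week follow-up, the 26-week treatment length and the schedule headings all support. For corticosteroids the two passages conflict if read literally, although a site would reasonably follow the dated, drug-specific rule in Section 3.4.5.

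The consequence is minor. It is confined to the Day 196 activity summaries and the interim that draws on them. A taper of about two weeks probably has a small effect in any one patient, and its frequency is unknown. A reader might go on to infer that the safety conclusions or the placebo comparison are compromised. They are not: the primary safety, pharmacokinetic and immunogenicity summaries are unaffected, and the placebo-controlled period ends before this window opens. The change is still worth making, because it costs little and the sponsor has already chosen Day 196 as the end date for corticosteroids.

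**What to change.** In the abstract and Sections 2.4.1 and 3.4.2, make the unchanged-dose rule run *through the Study Day 196 evaluation*, and allow tapering or stopping only *after the Study Day 196 evaluation*. Keep the exception for clinical deterioration. Section 3.4.5 can stay as it is, and the literal conflict over corticosteroids goes away.

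**Cost.** Two phrases in three places, with no new visits or data. Patients stay on their usual doses up to 14 days longer, and the tapering window shortens from 350 − 182 = 168 days to 350 − 196 = 154 days, as already set for corticosteroids. The amendment needs FDA submission and IRB/IEC approval (Section 10), so it is best carried in the next one.

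**Limit.** Section 1.5 reports 51 patients already dosed at its data cut, against 40 planned and up to 20 more. The new rule reaches only patients not yet past Day 182. For the others, report Day 196 activity with any background change since Day 182 flagged from the recorded concomitant medications.

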3.5 Schedule of Patient Evaluations

All patients who are assigned a PID and receive any study drug will be followed according to the protocol regardless of the number of doses of study drug received, unless consent for follow-up is withdrawn. The sponsor must be notified of all deviations from protocol visits or evaluations and these evaluations, if applicable, must be rescheduled or performed at the nearest possible time to the original schedule.

The schedule of patient evaluations for the screening and treatment periods can be found in Table 4, and the schedule of patient evaluations for the follow-up periods in the study can be found in Table 5. Eligibility screening will take place within 28 days before randomization into the study.

Patients will be instructed to call study personnel to report any abnormalities during the intervals between study visits and to come to the study site if medical evaluation is needed and the urgency of the situation permits. For emergency and other unscheduled visits to a medical facility other than the study site, medical records will be obtained by the investigator.

Table 4 Schedule of Patient Evaluations (Screening and Treatment Period)

Study Day	Visit	Screen ^b	Treatment Period													
			0	14	28	42	56	70	84	98 ^a	112	126	140	154	168	182
			1	2	3	4	5	6	7	8	9	10	11	12	13	14
ELIGIBILITY																
Written Informed Consent		X														
Verify Eligibility Criteria		X	X ^c													
Medical History ^d		X	X ^c													
Chest X-ray ^e		X														
Physical Examination		X	X ^c							X						
Body Weight			X							X						
ECG		X			X					X			X			
Tuberculosis Skin Test ^f		X														
HIV-1, HIV-2, Hepatitis A, B, C		X														
Serum βHCG ^g		X														
Urine βHCG ^g			X	X	X	X	X	X	X	X	X	X	X	X	X	X
STUDY DRUG ADMINISTRATION			X	X	X	X	X	X	X	X	X	X	X	X	X	X
SAFETY ASSESSMENT																
Vital Signs ^h		X	X	X	X	X	X	X	X	X	X	X	X	X	X	X
Assessment of AEs/SAEs		X	X	X	X	X	X	X	X	X	X	X	X	X	X	X
Serum Chemistry ^{i,j}		X	X ^c	X	X	X	X	X	X	X	X	X	X	X	X	X
CBC & Differentials, Platelets ^j		X	X ^c	X	X	X	X	X	X	X	X	X	X	X	X	X
Urinalysis ^j		X	X ^c	X	X	X	X	X	X	X	X	X	X	X	X	X
Serum for Safety Biomarkers ^k			X ^c													
Viral Surveillance Testing ^l			X ^c	X		X				X		X		X		
Record Concomitant Medications			X	X	X	X	X	X	X	X	X	X	X	X	X	X
DISEASE ACTIVITY AND DAMAGE																
Serum Levels of Muscle Enzymes ^{l,m}		X	X ^c	X	X	X	X	X	X	X	X	X	X	X	X	X
Strength in MMT		X	X ^c	X	X		X			X		X		X		
Extramuscular Activity Assessment (MDAAT)		X	X ^c	X		X				X		X		X		
Pulmonary Function Tests ⁿ		X								X ^o						
Physician Global Activity Assessment ^p		X	X ^c	X		X				X		X		X		
CLINHAQ ^q		X	X ^c	X		X				X		X		X		
Patient Global Activity Assessment ^q		X	X ^c	X		X				X		X		X		
Myositis Damage Index			X ^c							X						
SF-36v2			X ^c							X						
WPAI:SHP Questionnaire			X ^c							X						
Pruritus VAS ^r			X ^c	X		X				X		X		X		
CDASI ^r			X ^c	X		X				X		X		X		
DLQI ^r			X ^c							X						
Skin Photographs ^{r,s,t}			X ^c	X		X				X		X		X		

Table 4 Schedule of Patient Evaluations (Screening and Treatment Period)

Study Day	Visit	Screen ^b	Treatment Period													
			0	14	28	42	56	70	84	98 ^a	112	126	140	154	168	182
			1	2	3	4	5	6	7	8	9	10	11	12	13	14
CORRELATIVE STUDIES																
Serum for Exploratory Research and Storage ^{j, s}			X ^b		X		X			X		X		X		
Serum for autoantibodies ^j			X ^b							X						
Whole Blood for IFN Gene Expression Analyses		X	X ^b		X		X			X		X		X		
Peripheral Blood for Flow Cytometry ^{j, u}			X ^b							X						
Muscle Biopsy ^w			X ^b							X						
Punch Skin Biopsy ^{r, s}			X ^b							X						
Whole Blood for DNA Sample ^s				X												
PK/IM																
MEDI-545 Serum Level ^j			X ^v	X	X	X	X	X	X	X ^v	X	X	X	X	X	X ^v
Anti-MEDI-545 Antibodies ^j			X		X		X			X		X		X		

Table 4 Footnotes:

- a. If a patient discontinues his or her participation in the study prior to Study Day 98, the assessments designated for Study Day 98 will be performed at the discontinuation visit. If a particular assessment has been performed within 2 weeks before the discontinuation visit, it need not be repeated, except if follow-up muscle and skin biopsies have been done at any time, they need not be repeated. (If a patient discontinues after Day 98, see Table 5 footnotes a and b.)
- b. Obtain within 28 days prior to Study Day 0.
- c. Assessments may be performed up to 72 hours prior to dosing on Study Day 0, except muscle and skin biopsies and skin photographs, which may be performed up to 28 days prior to Study Day 0. The open muscle biopsy may be done as part of screening to meet inclusion criteria as long as the dose(s) of immunosuppressive medications have been stable for one month and will remain the same as that in Day 0.
- d. Medical history includes history of viral reactivation events.
- e. Chest x-ray taken within 6 months of screening is considered suitable for screening and need not be repeated.
- f. Do not administer TB skin test if the patient is known to be positive.
- g. Women, unless surgically sterile or at least 2 years postmenopausal, must have a negative serum pregnancy test within 28 days before randomization/entry, and a negative urine pregnancy test on all dosing visits before receiving the study drug.
- h. Vital signs include heart rate, blood pressure, respiratory rate and temperature. Blood pressure should be obtained with the patient in the position to be used for drug administration. Vital signs will be monitored up to 30 minutes before dosing, approximately every 15 minutes during administration of the drug, immediately after the infusion (within 10 minutes after the infusion has stopped), and approximately every 30 minutes after the completion of the infusion until stable, as judged by the investigator. Blood pressure and heart rate will also be taken prior to discharge from the site on visits in which study drug is administered.
- i. Includes Na, K, Cl, bicarbonate, BUN, creatinine, bilirubin, alkaline phosphatase, and random glucose.

- j. Obtained prior to study drug administration, where applicable. Viral surveillance includes testing for EBV, CMV, HSV, and HPV. The patient will provide self-collected vaginal swabs for HSV and HPV testing; the swabs may also be collected by an MD/OBGYN or qualified medical personnel such as an appropriately trained nurse practitioner, if approved by the sponsor.
- k. A serum sample for assessment of safety biomarkers (including serum levels of mast cell tryptase, cytokines/chemokines, and IgE antibodies) will be collected in all patients prior to study drug administration on Study Day 0 and in any patient with a Grade 1 or higher infusion reaction as soon as possible after the event, 60 minutes after the event, and at discharge (see Section 3.4.4 for details).
- l. At selected sites only.
- m. Serum muscle enzymes include CK, aldolase, AST, ALT, and LDH.
- n. Pulmonary function tests, a part of MDAAT, will assess lung volumes and diffusion capacity for carbon monoxide (DLCO).
- o. Pulmonary function test on Study Day 98 should be done within 7 days before the visit.
- p. Physician Global Activity Assessment is included as part of MDAAT.
- q. Patient Global Activity Assessment is included as part of CLINHAQ.
- r. DM patients only.
- s. Optional procedures.
- t. Photographs of up to two target skin lesions (if present) are requested. One photograph should be of the skin lesion that will be biopsied. It is preferred that the photographs are taken prior to the punch skin biopsy.
- u. Flow cytometry will be performed on peripheral blood samples from selected sites in North America.
- v. On Study Days 0, 98 and 182 only, serum samples for MEDI-545 concentrations are collected immediately before, immediately after (within 10 minutes after the infusion has stopped), and 2 hours after administration of the IV infusion.
- w. Open muscle biopsy, unless otherwise approved by the sponsor.

Table 5 Schedule of Patient Evaluations (Follow-up Period)

Study Day Visit	Follow-up Period								
	185	189	196 ^a	210	238	266	294	322	350 ^b
	15	16	17	18	19	20	21	22	23
SAFETY ASSESSMENT									
Physical Examination			X						X
Body Weight			X						X
ECG			X						X
Urine βHCG						X			X
Vital Signs ^c	X	X	X	X	X	X	X	X	X
Assessment of AEs/SAEs	X	X	X	X	X	X	X	X	X
Serum Chemistry ^d			X	X	X	X	X	X	X
CBC & Differentials, Platelets			X	X	X	X	X	X	X
Urinalysis			X	X	X	X	X	X	X
Viral Surveillance Testing			X			X			X
Record Concomitant Medications			X	X	X	X	X	X	X
DISEASE ACTIVITY AND DAMAGE									
Serum Levels of Muscle Enzymes ^f			X	X	X	X	X	X	X
Strength in MMT			X		X		X		X
Extramuscular Activity Assessment (MDAAT)			X		X		X		X
Pulmonary Function Tests ^g			X						X
Physician Global Activity Assessment ^h			X		X		X		X
CLINHAQ ⁱ			X		X		X		X
Patient Global Activity Assessment ⁱ			X		X		X		X
Myositis Damage Index			X						X
SF-36v2			X						X
WPAI:SHP Questionnaire			X		X		X		X
Pruritus VAS ^j			X		X		X		X
CDASI ^j			X		X		X		X
DLQI ^j			X		X		X		X
Skin Photographs ^{j,k,l}			X		X		X		X
CORRELATIVE STUDIES									
Serum for Exploratory Research and Storage			X		X		X		X
Serum for Autoantibodies			X						X
Whole Blood for IFN Gene Expression Analyses			X		X		X		X
Peripheral Blood for Flow Cytometry ^m			X		X		X		X
PK/IM									
MEDI-545 Serum Level	X	X	X	X	X	X	X	X	X
Anti-MEDI-545 Antibodies			X		X		X		X

Table 5 Footnotes:

- a. If a patient discontinues after Study Day 98 and prior to Study Day 196, the evaluations scheduled for Study Day 196 must be completed. If a particular assessment has been performed within 2 weeks before the discontinuation visit, it need not be repeated.
- b. If a patient discontinues after Study Day 196 and prior to Study Day 350, the evaluations scheduled for Study Day 350 must be completed. If a particular assessment has been performed within 2 weeks before the discontinuation visit, it need not be repeated.
- c. Vital signs include heart rate, blood pressure, respiratory rate and temperature.
- d. Includes Na, K, Cl, bicarbonate, BUN, creatinine, bilirubin, alkaline phosphate, and random glucose.
- e. At selected sites only.
- f. Serum muscle enzymes include CK, aldolase, AST, ALT, and LDH.
- g. Pulmonary function tests, a part of MDAAT, will assess lung volumes and DLCO.
- h. Physician Global Activity Assessment is included as part of MDAAT.
- i. Patient Global Activity Assessment is included as part of CLINHAQ.
- j. DM patients only.
- k. Optional procedures.
- l. Photographs of up to two target skin lesions (if present) are requested. One photograph should be of the skin lesion that was biopsied.
- m. Flow cytometry will be performed on peripheral blood samples from selected sites in North America.

Screening

Note: All screening laboratory assessments must be performed within 28 days before randomization (Study Day 0). The screening evaluations may be carried out over more than one visit. Chest x-ray taken within 6 months of screening is considered suitable for screening and need not be repeated.

1. Written informed consent
2. Verify eligibility criteria
3. Screening medical history
4. Chest x-ray
5. Screening physical examination
6. Screening ECG
7. TB skin test
8. Vital signs (temperature, blood pressure, pulse rate, respiratory rate)
9. Urinalysis
10. Blood collection for screening
 - Chemistry panel (including Na, K, Cl, bicarbonate, BUN, creatinine, bilirubin, alkaline phosphatase, and random glucose)
 - CBC with differential and platelet count
 - Serum for hepatitis A antibody, hepatitis B surface antigen, hepatitis C antibody and HIV-1 and HIV-2 antibodies
 - Serum β HCG (for women who are sexually active and are not surgically sterile or at least 2 years postmenopausal; this test must be negative for study participation)
 - Serum levels of muscle enzymes (including CK, aldolase, LDH, ALT, and AST)
 - Whole blood for IFN gene expression analysis
11. Disease activity assessments:
 - MMT for strength
 - Extramuscular activity assessment (based on MDAAT scales)
 - Pulmonary function tests
 - Physician global activity assessment (included as part of MDAAT)
 - CLINHAQ (includes Patient global activity assessment)

Study Day 0: First Dose

Visit 1

1. Verify eligibility criteria
2. Update screening history and physical examination (any new findings since screening)
3. Body weight
4. Randomization and assignment of PID
5. Record concomitant medications
6. Urinalysis, includes collection of urine for β HCG (for women who are sexually active and are not surgically sterile or at least 2 years postmenopausal; this test must be negative for study participation)
7. Baseline blood collection
 - Chemistry panel

- CBC with differential and platelet count
 - Serum for safety biomarkers
 - Serum levels of muscle enzymes
 - Serum for exploratory research (including IFN- α assay and proteomics) and storage
 - Serum for autoantibodies (including ANA, anti-SSA, anti-RNP, anti-Jo-1, anti-SRP, anti-Mi-2 antibodies)
 - Whole blood for IFN gene expression analysis
 - Peripheral blood for flow cytometry
 - MEDI-545 serum level
 - Anti-MEDI-545 antibodies
8. Viral surveillance testing (including EBV, CMV, HSV, and HPV)
 9. Disease activity assessments:
 - MMT
 - Extramuscular activity assessment
 - Physician global activity assessment (included as part of MDAAT)
 - CLINHAQ (includes Patient global activity assessment)
 - Myositis Damage Index
 - SF-36v2
 - WPAI: SHP questionnaire
 - Pruritus VAS (DM patients only)
 - CDASI (DM patients only)
 - DLQI (DM patients only)
 10. Skin photographs (optional, DM patients only, preferably prior to the punch skin biopsy and within 28 days before the visit)
 11. Muscle biopsy (within 28 days before the visit). The open muscle biopsy may be done during screening to address inclusion criteria as long as the dose(s) of immunosuppressive medications have been stable for one month and will remain the same as that in Day 0. Muscle for IFN gene expression analysis
 12. Punch skin biopsy (optional punch biopsy, DM patients only, within 28 days before the visit). Skin for IFN gene expression analysis
 13. Vital signs up to 30 minutes before administration of study drug
 14. Administration of study drug
 15. Monitor vital signs approximately every 15 minutes during administration of the drug, immediately after the infusion (within 10 minutes after the infusion has stopped), and approximately every 30 minutes after the completion of the infusion until stable. Measure blood pressure and heart rate prior to discharge from the site.
 16. Post-dose blood collection (within 10 minutes after the infusion has stopped and 2 hours after study drug administration)
 - MEDI-545 serum level
 17. AE/SAE assessment

Study Days 14, 42, 70, 84, 112, 140, 168 (\pm 3 Days): Treatment Period

Visits 2, 4, 6, 7, 9, 11, 13

1. Record concomitant medications

2. Urinalysis includes collection of urine for β HCG (for women who are sexually active and are not surgically sterile or at least 2 years postmenopausal)
3. Blood collection
 - Chemistry panel
 - CBC with differential and platelet count
 - Serum levels of muscle enzymes
 - MEDI-545 serum level
 - Whole blood for DNA sample on Study Day 14 only (optional)
4. ECG (Study Days 42, 98, and 140)
5. Vital signs up to 30 minutes before administration of study drug
6. Administration of study drug
7. Monitor vital signs approximately every 15 minutes during administration of the drug, immediately after the infusion (within 10 minutes after the infusion has stopped), and approximately every 30 minutes after the completion of the infusion until stable. Measure blood pressure and heart rate prior to discharge from the site.
8. AE/SAE assessment

Study Days 28, 56, 126, 154 (\pm 3 Days): Treatment Period

Visits 3, 5, 10, 12

1. Record concomitant medications
2. Urinalysis includes collection of urine for β HCG (for women who are sexually active and are not surgically sterile or at least 2 years postmenopausal)
3. Baseline blood collection
 - Chemistry panel
 - CBC with differential and platelet count
 - Serum levels of muscle enzymes
 - Serum for exploratory research (including IFN- α assay and proteomics) and storage
 - Whole blood for IFN gene expression analysis
 - MEDI-545 serum level
 - Anti-MEDI-545 antibodies
4. Viral surveillance testing
5. Disease activity assessments:
 - MMT
 - Extramuscular activity assessment
 - Physician global activity assessment (included as part of MDAAT)
 - CLINHAQ (includes Patient global activity assessment)
 - Pruritus VAS (DM patients only)
 - CDASI (DM patients only)
6. Skin photographs (optional, DM patients only, within 7 days of the visit)
7. Vital signs up to 30 minutes before administration of study drug
8. Administration of study drug
9. Monitor vital signs approximately every 15 minutes during administration of the drug, immediately after the infusion (within 10 minutes after the infusion has stopped), and

approximately every 30 minutes after the completion of the infusion until stable. Measure blood pressure and heart rate prior to discharge from the site.

10. AE/SAE assessment

Unscheduled Visit

Evaluations may be performed during unscheduled visits as deemed warranted by the investigator.

Study Day 98 (± 3 Days) or Discontinuation Visit

If a patient discontinues the study prematurely prior to Study Day 98, he or she should return to the study site and complete the following evaluations. If a particular assessment has been performed within 2 weeks before the discontinuation visit, it need not be repeated.

Visit 8

1. Record concomitant medications
2. Physical examination
3. Body weight
